Study Design: The study is a randomized Phase II, four arm treatment trial. The primary purpose of the study is to define new agents with promising activity against acute GVHD suitable for testing against corticosteroids alone in a subsequent Phase III trial.

Corticosteroids have been used as primary therapy for acute GVHD for many years. Historical published and unpublished data from the University of Minnesota, Dana Farber Cancer Institute and the Fred Hutchinson Cancer Center define an expected 35% complete response (CR) at Day +28 of corticosteroid therapy for previously untreated patients with acute GVHD.

In this trial, patients with newly diagnosed acute GVHD will receive corticosteroids plus one of four new agents. A control arm of only corticosteroids will not be employed. Each agent will be assessed for safety (stopping rules defined) and efficacy ($\geq 35\%$ CR rate at Day 28 of therapy).

Primary Objective: The primary objective is to estimate the proportion of CR at Day 28 of therapy for newly diagnosed acute GVHD for each of these agents given in combination with corticosteroids.

Secondary Objectives: Secondary objectives are to determine: proportion of partial response (PR), mixed response and progression at Day 28; proportion of treatment failure (no response, progression, administration of additional therapy for GVHD, or mortality) by Day 14; the incidence of GVHD flares requiring increasing therapy before Day 90. In addition, the following endpoints will be examined: incidence of discontinuation of immune suppression without flare by Days 90, 180 and 270 post-therapy, incidence of chronic GVHD by 9 months, overall survival at 6 and 9 months post initiation of therapy, incidence of systemic infections within 3 months of initiation of therapy, incidence of EBV-associated lymphoma.

Eligibility: Patients must be greater than or equal to 6 years of age and have acute GVHD requiring systemic therapy. No previous systemic immune suppressive therapy for acute GVHD is allowed except for a maximum 48 hours of prior corticosteroid therapy (≥ 1 mg/kg/day methylprednisolone). Patients receiving ONTAK, pentostatin, or etanercept within 7 days of screening will be excluded. Patients receiving MMF for GVHD prophylaxis will be randomized into one of the other three treatment arms. Patients must have an absolute neutrophil

count (ANC) greater than 500/ μ L and an estimated creatinine clearance greater than 30 mL/minute.

Treatment Description: The treatment schedules are as follows: **Etanercept** [25 mg subcutaneously twice weekly for up to 4 weeks; discontinue if in CR by 4 weeks]. Mycophenolate mofetil (**MMF**) [20 mg/kg (maximum 1 gm) PO or IV BID; continue through prednisone taper, then taper MMF over 4 weeks]. Denileukin Diftitox (**ONTAK®**) [9 mcg/kg IV Days 1, 3, 5, 15, 17, 19]. **Pentostatin** [1.5 mg/m² daily for 3 days; Days 1-3 and repeat Days 15-17].

All patients will receive methylprednisolone 2 mg/kg/day IV (or prednisone 2.5 mg/kg/day PO) divided in 2-3 daily doses for at least 7 days. Prednisone may be tapered as tolerated to no less than 0.75 mg/kg/day (methylprednisolone 0.6 mg/kg/day) at Day 28 of therapy. If not in CR at Day 28, patients will be followed for study endpoints, but assigned therapy can be continued or changed per institutional guidelines.

In addition to prescribed study drug plus corticosteroids, all patients should receive transfusion support per institutional practice; anti-infective prophylaxis directed towards CMV, gram positive (encapsulated) bacteria, pneumocystis carinii and fungal infections

[figure not shown]
Weekly GVHD organ stage scores, overall clinical grade, biopsy information for GVHD and relevant differential diagnosis will be recorded and reported to the BMT CTN Data Coordinating Center (DCC).

Accrual Objective: A maximum of 180 patients, but at most 65 per arm, will be randomized to one of the four treatment arms. After 80 patients are evaluable for the primary endpoint, if in any experimental arm, observed responses suggest a posterior probability > 85% that an arm will have a true CR < 35%, enrollment to the arm will cease and the arm will be excluded from further consideration due to lack of evidence for efficacy.

Accrual Period: The estimated accrual period is 12 months.

Study Duration: Patients will be followed for 9 months following initiation of therapy.

STUDY DESIGN SCHEMATIC

* Steroids = 2.5 mg/kg prednisone/day PO or IV equivalent in methylprednisolone (2 mg/kg) divided 2-3 times daily

Primary Endpoint:
Proportion of CR at Day 28 of therapy.

STUDY SCHEMA

Aim: To determine if any of four new agents, given in addition to corticosteroids as initial therapy for acute GVHD improves response rate and overall clinical outcome.

Inclusion Criteria	Exclusion Criteria

 1. Prior allogeneic hematopoietic stem cell transplant using either bone marrow, PBSC or cord blood. 2. De novo acute GVHD diagnosed within 48 hours prior to enrollment. Biopsy confirmation of GVHD is strongly recommended but not required. Enrollment should not be delayed awaiting biopsy or pathology results. The patient must have had no previous systemic immune suppressive therapy given for treatment of acute GVHD except for a maximum 48 hours of prior corticosteroid therapy (≥ 1 mg/kg/day methylprednisolone). 3. GVHD developing following DLI for prophylaxis or planned DLI. 4. ≥ 6 years of age at enrollment. 5. Clinical status at enrollment to allow tapering of steroids to not less than 0.6 mg/kg/day methylprednisolone (0.75 mg/kg/day prednisone) at Day 28 of therapy (e.g. persisting malignant disease suggesting the need for accelerated taper of immunosuppression). 6. ANC greater than 500/μL. 7. Estimated creatinine clearance greater than 30 mL/minute 8. Signed informed consent and/or assent. 9. Assent and educational materials provided to, and reviewed with, patients under the age of 18. 	
 1. ONTAK, pentostatin or etanercept given within 7 days of enrollment. 2. Isolated limited skin GVHD as the sole manifestation of acute GVHD. 3. Active uncontrolled infection. 4. Patients that have undergone an unscheduled (or not part of original transplant therapy plan) DLI. 5. Patients unlikely to be available at the transplant center on Day 28 and 56 of therapy. 6. A clinical syndrome resembling de novo chronic GVHD developing at any time after allotransplantation. 7. Other investigational therapeutics for GVHD within 30 days, including agents used for GVHD prophylaxis. 8. If any prior steroid therapy (for indication other than GVHD), treatment at doses > 0.5 mg/kg/d methylprednisolone within 7 days prior to onset of GVHD. 9. Patients who are pregnant, breast feeding, or if sexually active, unwilling to use effective birth control for the duration of the study. 10. Adults unable to provide informed consent 11. Patients with a history of intolerance to any of the study drugs.

If any improvement after 7 days of full dose corticosteroids + study drug: Taper steroids as tolerated to no less than 0.75 mg/kg/day prednisone (or 0.6 mg/kg/day methylprednisolone) on Day 28. Improvement is defined as any clinically recognizable lessening of skin rash, redness, or extent; lessening of diarrhea or lowered bilirubin (though it does not have to be greater than or equal to one stage improvement in any involved organ), without worsening in any organ.

Suggested prednisone taper for responders (round to nearest 5 mg of prednisone):
 
2.5 mg/kg/day divided in 2-3 doses Day 0-6 2.5 mg/kg/day once daily Day 7-13 2 mg/kg/day Day 14-21 1.4 mg/kg/day Day 21-28 0.75 mg/kg/day Day 29-35 0.6 mg/kg/day Day 36-42 0.4 mg/kg/day Day 43-49 0.25 mg/kg/day Day 50-56 0.1 mg/kg/day Day 57-63 0.1 mg/kg every other day, Day 63-69; Discontinue on Day 70
	
Primary endpoint: Proportion of CR at Day 28 of therapy
 
Secondary endpoints:
 
 - Proportion of PR, mixed response and progression at Day 28 - Proportion of NR, progression, administration of additional therapy for GVHD, or mortality by Day 14 - Incidence of GVHD flares requiring increasing therapy before Day 90 - Incidence of discontinuing immune suppression without flare by Day 90, 180 and 270 post therapy - Incidence of Chronic GVHD by 9 months - Survival at 6 and 9 months after initiation of treatment - Incidence of systemic infections within 3 months of therapy - Incidence of EBV lymphoma within 9 months of therapy
--	---

If acute GVHD progresses within 7 days or no response within 14 days, then treat with alternative secondary GVHD therapy off study, but follow for study endpoints.

TABLE OF CONTENTS

1	BACKGROUND AND RATIONALE.....	1-1
1.1	Study Goal	1-1
1.2	Background Data: Therapy of Acute GVHD	1-2
1.2.1	Daclizumab	1-2
1.2.2	Infliximab	1-2
1.2.3	Etanercept	1-2
1.2.4	Sirolimus.....	1-3
1.2.5	Mycophenolate Mofetil (MMF).....	1-3
1.2.6	Pentostatin.....	1-3
1.2.7	Denileukin Diftitox (ONTAK).....	1-3
1.2.8	Study Agents.....	1-4
1.2.9	Staging of Acute GVHD.....	1-4
2	STUDY DESIGN.....	2-1
2.1	Study Design	2-1
2.2	Primary Objective and Rationale for Study Design	2-1
2.3	Eligibility	2-2
2.3.1	Inclusion Criteria.....	2-2
2.3.2	Exclusion Criteria.....	2-4
2.3.3	Informed Consent.....	2-5
2.4	Treatment Plan.....	2-5
2.4.1	Risks of All Study Drugs	2-5
2.4.1.1	Risks of infection	2-5
2.4.1.2	Drug associated toxicities.....	2-5

1 BACKGROUND AND RATIONALE

Acute graft-versus-host disease (GVHD) is the major complication of allogeneic hematopoietic stem cell (HSC) transplantation. Acute GVHD produces significant morbidity and complicates patient management resulting in organ toxicity, frequent infections, malnutrition and substantial delay in recovery from transplantation.

Acute GVHD usually occurs within the first 30-60 days of allogeneic HSCT and may involve the skin, liver and intestinal tract. T lymphocytes contained in the donor graft respond *in vivo* to disparate major (HLA) or minor (non-HLA) histocompatibility antigens on host tissues and a cascade of events leads to the signs and symptoms of acute GVHD. Greater HLA disparity between the donor and the recipient results in a higher incidence of acute GVHD.

The syndrome of acute GVHD includes the following signs and symptoms. Skin involvement (maculopapular exanthem) is usually the first sign of acute GVHD. Lesions may be pruritic or painful, red to violaceous in color, and often involve the palms and soles. Acute GVHD of the intestines may involve the stomach, small bowel and colon producing persistent nausea and vomiting or profuse diarrhea, intestinal bleeding, crampy abdominal pain and ileus. Liver GVHD produces cholestatic liver injury with hyperbilirubinemia and some hepatocellular enzyme elevations.

The use of cyclosporine (CSA) or tacrolimus (FK) plus short course methotrexate (MTX) has lowered the risk for acute GVHD compared to single agent or other combination therapy, but still 35-50% of patients develop Grade 2-4 acute GVHD [2-4, 5]. Older recipients or those transplanted from alternative (unrelated or partially matched) donors may develop more frequent or possibly more therapy-resistant acute GVHD.

GVHD Therapy

Corticosteroids have been the primary therapy for acute GVHD for over three decades. Various additional immunosuppressive strategies have been tested as GVHD therapy but neither anti-thymocyte globulin (ATG), CD5-immunotoxins, IL-1 antagonists nor other agents have been demonstrably helpful in either control of GVHD symptoms or improvement in survival [6-11]. Published response rates of complete response (CR) to acute GVHD therapy with corticosteroids range from 25-41% [12-14]. These rates will be used as benchmarks for assessing efficacy of promising new agents. New immunosuppressive agents and strategies are required to improve the management of GVHD and decrease the toxicities of the immunosuppressive regimens.

1.1 Study Goal

This study will test four new agents (etanercept, MMF, denileukin diftitox (ONTAK) and pentostatin), each in combination with corticosteroids as initial therapy of acute GVHD in a prospective, randomized Phase II trial. The primary purpose of the study is to identify agents

with sufficient promise for definitive testing in a subsequent Phase III trial in comparison to corticosteroids alone.

1.2 Background Data: Therapy of Acute GVHD

Recently, several new agents have been tested for GVHD therapy. Relevant data (peer-reviewed manuscripts, abstracts and/or personal communication) about the most promising new agents are briefly summarized below.

1.2.1 Daclizumab

A report from Germany [15] summarized GVHD treatment in 16 patients; 12 had steroid resistant acute GVHD. Patients (n=7) received daclizumab in a dosage of 1 mg/kg body weight (BW) on Day 1-5 and once every week thereafter until Day 28. Eight patients received 1 mg/kg on Day 1 and 2, followed by one dose per week through Day 28. Of the 12 evaluable patients, 6 responded to therapy. However, the rate of infections was high with 14 of 16 patients experiencing infections, 2 of them fatal. Four of 16 (25%) patients survived.

Przepiorka et al., [16] reported on 43 patients with steroid refractory acute GVHD. Daclizumab was administered at 1 mg/kg IV on study Day 1, 8, 15, 22 and 29 (n=24) or at 1 mg/kg IV on study Day 1, 4, 8, 15 and 22 (n=19) given either weekly (n=29) or 3 times per week (n=19). CR at Day 42 was 29% using the weekly regimen and 47% using the 3 times per week regimen. Improved 120 day survival (29% versus 53%) was also seen with the second regimen.

Wolff [17] reported a study of 12 patients treated with daclizumab and steroids. Six patients achieved CR, 4 partial responses, 1 non-response and 1 early death. A randomized trial of daclizumab plus corticosteroids versus corticosteroids alone (Dana Farber/ Minnesota/other centers) showed no benefit and some added toxicity with daclizumab [42].

1.2.2 Infliximab

Couriel et al., [18] reported a preliminary analysis of a randomized trial (n=60) showing no benefit of infliximab over steroids alone. The trial was stopped early. However, Sleight et al. [19] reported a series of 24 pediatric patients with 16 of the patients refractory to steroids. In this series, the patients received infliximab plus various other therapies. Improvement was seen in 15/16 evaluable patients with skin GVHD, 11/14 with gut GVHD, and 1/3 with liver GVHD; only 2 of 16 are surviving. Kobbe et al. [20] reported PR in 3 of 4 patients receiving 10 mg/kg/week.

1.2.3 Etanercept

In a report of 10 patients with chronic GVHD, Chiang et al. [21] found improvement of GVHD in 7 of the 8 patients completing an 8-week course. In another series, 13 patients received 25 mg subcutaneously twice weekly for up to 8 weeks [22]. Ten of 13 had a CR, most within 2 weeks. CR was more frequent for Grade 2 than Grade 3 acute GVHD.

1.2.4 Sirolimus

Benito et al. [23] reported 21 cases of steroid refractory disease treated with sirolimus at a median of 37 days post-transplant. Ten patients stopped treatment early (5 NR, 2 myelosuppression, 2 seizures). Ten patients had thrombotic microangiopathy (TMA). However, in 5 of 10, TMA did not appear correlated with sirolimus therapy. Of the 18 patients who received at least 6 doses, 12 responded (5 CR and 7 PR). Six of the 21 patients are surviving. [[name], personal communication]. It is recognized that sirolimus has complex pharmacology and drug interactions. The formulation is currently not suitable for concurrent use with voriconazole. Information on dose modifications required for combined use of sirolimus and voriconazole may be available during 2004. It is promising but additional clinical pharmacology is needed.

1.2.5 Mycophenolate Mofetil (MMF)

Basara et al. [24] reported that treatment with MMF improved GVHD in 65% of 17 patients with acute GVHD (N=24; 17 acute GVHD; 65% improved). A report from Seattle ([name] personal communication) showed similar results with 6 CR and 2 PR in 19 patients.

1.2.6 Pentostatin

Bolanos-Meade et al. [25] reported a dose escalation trial for treatment of steroid resistant acute GVHD using 1-4 mg/m² daily x 3 days. The best dose was 1.5mg/m² x 3 days, then repeated q 2 weeks. Of 20 treated patients, 11 achieved CR, 3 achieved PR, 3 had mixed responses and 3 progressed while on therapy. A recent update (personal communication, [name]) totaling 23 treated patients showed 14 CR and 3 PR among 22 evaluable patients. At higher doses, late infections were considered dose limiting. The drug was well tolerated with only modest elevations of liver function tests and thrombocytopenia, each observed in only a single patient.

1.2.7 Denileukin Diftitox (ONTAK)

Shaughnessy et al. [26] described 11 patients treated with ONTAK 4.5 µg/kg/d x 5 days followed by the same dose weekly x 4. Of the 11, there were 5 responders, including 2 CR and 1 PR with 2 lesser responses.

Ho et al. reported 10 patients receiving 9 mcg/kg IV Days 1, 15 or Days 1, 3, 5, 15, 17 and 19. CR was seen in 3 patients, PR in 4 and mixed response in 2 (78% CR+PR). A subsequent update [27] included 28 patients with steroid refractory GVHD [grade II (n = 10), grade III (n = 13), grade IV (n = 5)]. Seven received ONTAK at dose level I (9 µg/kg IV on Days 1 and 15), 16 at dose level II (9 µg/kg IV Days 1, 3, 5, 15, 17 and 19), and 5 at dose level III (9µg/kg IV Days 1-5, 15-19), which yielded dose-limiting toxicity (1 acute renal failure, 3 elevated hepatic transaminases). At Day 28, 7 of 22 evaluable (32%) had CR and 9 (41%) PR, for an overall response rate of 73%. Among the 9 with PR, 3 additional patients subsequently entered CR after Day 29 without additional GVHD therapy, resulting in an overall CR rate of 45%. Response rate was highest at dose level II (CR = 45% and PR = 27%). Of the 22 evaluable for GVHD response, 9 (41%) are alive.

1.2.8 Study Agents

Based on the available data presented above, the four agents considered most promising for Phase II multi-center testing were etanercept, MMF, ONTAK and pentostatin. Each study agent has promising preliminary data reported from single or several center studies, suitable safety experience and tolerable applicability for multi-center Phase II testing as initial systemic therapy for acute GVHD.

1.2.9 Staging of Acute GVHD

Several schemas for staging and grading of acute GVHD have been published [28, 41]. In this study we will classify patients by the CIBMTR grading schema (Grades A-D), which has been shown to be more predictive of survival than earlier versions [7, 28].

CHAPTER 2

2 STUDY DESIGN

2.1 Study Design

This trial is designed to evaluate the safety and efficacy of four new agents for acute GVHD in a prospective, multi-center, two-stage, randomized, four-arm Phase II trial. Each study arm will include corticosteroids plus a new agent. After 80 patients are evaluable for the primary endpoint, each arm will be assessed for safety using Bayesian posterior probability rules.

Study Design without Steroid Only Control

In this Phase II trial design, a corticosteroid only control arm will not be used since such an arm would not aid in judging which experimental arm was suitable for consideration in a subsequent Phase III randomized trial given the limited statistical power for comparison between arms. Each agent will be tested for potential efficacy against well established historical data published from several centers ($\geq 35\%$ CR rate at Day 28 of therapy). A control cohort would not assist this comparison and would delay completion of this prospective Phase II test of individual agents given as an adjunct to corticosteroids.

2.2 Primary Objective and Rationale for Study Design

The primary purpose of the study is to define new agents with promising activity against acute GVHD suitable for testing against corticosteroids alone in a subsequent comparative, Phase III trial. Careful review of published and unpublished data on therapy of acute GVHD documents an expected complete response (CR) rate for steroids alone of 35%. Each of the four study agents selected are reported to have promising activity as therapy of acute GVHD in preliminary testing but have limited Phase II data available. This trial will more formally test their safety and efficacy as supplemental to corticosteroids alone.

The choice of agents for study in the subsequent Phase III trial against steroids alone will include consideration of the initial CR rate (the primary endpoint) as well as several important assessments of other safety and efficacy parameters (the secondary endpoints). Those considered suitable for subsequent testing will have demonstrable primary efficacy as well as satisfactory estimates (developed within this randomized Phase II trial) of GVHD control without excessive rates of the anticipated complications of infection, GVHD flare, chronic GVHD or early mortality. Thus, in this Phase II trial, a control arm will be omitted and deferred until the formal, prospective Phase III trial, which will test the best agent(s) against the control of steroids alone.

2.3 Eligibility

2.3.1 Inclusion Criteria

Biopsy of involved tissue is strongly encouraged, but not required for study entry. The clinical diagnosis of acute GVHD requiring systemic therapy with corticosteroids is necessary for enrollment on the trial. Enrollment and randomization includes commitment to continue both steroids and study drug as indicated by the protocol as well as the required follow-up observations. If the intention to treat a patient is dependent on histologic results, the patient should not be enrolled on the BMT 0302 study until the results are known. Patients should only be enrolled with a clinically established diagnosis. Histologic confirmation of acute GVHD is not required, but can be used as supportive evidence for the diagnosis. If an unexpected biopsy result occurs, the center should contact the protocol chair.

1. Prior allogeneic hematopoietic stem cell transplant using either bone marrow, peripheral blood stem cells or cord blood. Recipients of non-myeloablative transplants are also eligible.
2. De novo acute GVHD requiring systemic therapy within 48 hours of diagnosis [28]. GVHD is defined as the presence of skin rash and/or persistent nausea, vomiting, and/or diarrhea and/or cholestasis as the clinical criteria compatible with the diagnosis of acute GVHD when present in the right clinical setting and not directly attributable to other etiologies such as drug rash, enteric infection, or hepatotoxic syndromes (e.g., veno occlusive disease of the liver). The patient must have had no previous systemic immune suppressive therapy given for treatment of acute GVHD except for a maximum 48 hours of prior corticosteroid therapy ≥ 1 mg/kg/day methylprednisolone.

Note that patients with stage II skin or isolated upper gastrointestinal (GI) only are eligible. However, the protocol team does not recommend initiating systemic therapy with steroids for limited skin or upper GI only GVHD, but if the institutional treatment plan and treating physician initiates corticosteroid therapy at ≥ 2.0 mg/kg/day methylprednisolone (2.5 mg/kg/day prednisone), the patients are eligible for enrollment.

3. Patients that have undergone a donor lymphocyte infusion (DLI) as part of their original transplant therapy plan.
4. Greater than or equal to 6 years of age at the time of enrollment.
5. Clinical status at enrollment to allow tapering of steroids to not less than 0.6 mg/kg/day methylprednisolone (0.75 mg/kg/day prednisone) at Day 28 of therapy.
6. Absolute neutrophil count (ANC) greater than 500/ μ L.
7. Estimated creatinine clearance greater than 30 mL/minute (see Table 2.3.1).
8. Written informed consent and/or assent from patient, parent or guardian.

9. Documentation that the assent document and education materials have been provided to, and reviewed with, patients under the age of 18.

Table 2.3.1
ESTIMATED CREATININE CLEARANCE (mL/min)

Serum Creatinine	Ideal Body Weight 20 kg 10 years/15	40 kg 20years/30/40	60 kg 20years/30/40	80 kg 20years/30/40	100 kg 20years/30/40
0.8	Male 45/43 Female 38/37	Male 83/76/69 Female 71/65/59	Male 125/115/104 Female 106/97/89		
1.0	Male 36/35 Female 31/30	Male 67/61/56 Female 57/52/47	Male 100/92/83 Female 85/78/71		
1.2	Male 30/29 Female 26/25	Male 56/51/46 Female 47/43/39	Male 83/76/83 Female 59/65/71	Male 111/102/93 Female 94/87/79	
1.4	Male 26/25 Female 22/21	Male 48/44/40 Female 41/37/34	Male 71/66/60 Female 51/56/51	Male 95/87/79 Female 81/74/68	Male 119/109/99 Female 101/93/84
1.6	Male 23/22 Female 19/18	Male 42/38/35 Female 35/33/30	Male 63/57/52 Female 53/49/44	Male 83/76/69 Female 71/65/59	Male 104/96/87 Female 89/81/74
1.8	Male 20/19 Female 17/16	Male 37/34/31 Female 32/29/26	Male 56/51/46 Female 47/43/39	Male 74/68/62 Female 63/58/53	Male 93/85/77 Female 79/72/66
2.0	Male 18/17 Female 15/15	Male 33/31/28 Female 28/26/24	Male 50/46/42 Female 43/39/35	Male 67/61/56 Female 57/52/47	Male 83/76/69 Female 71/65/59
2.2		Male 30/28/25 Female 26/24/22	Male 46/42/38 Female 39/35/32	Male 61/56/51 Female 52/47/43	Male 76/69/63 Female 64/59/54

Note: Modified from Cockcroft Gault equation; $(140 - \text{age}) * \text{wt} / ([\text{Cr}] * 72) = \text{clearance}$ Females: 0.85 x the calculated result.

Calculated or measured creatinine clearance for patients can also be used.

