2.4.5.6 Guidelines for dose adjustment

Myelosuppression: If the ANC is less than 1000/µL, pentostatin dosing should be reduced by 50%. If the ANC is less than 500/µL, the drug should be discontinued until neutrophil recovery occurs. Use of filgrastim and/or discontinuation of other myelosuppressive agents is allowed.

Renal Insufficiency: Pentostatin dose reductions for renal insufficiency are made based on estimated creatinine clearance (Table 2.3.1). For clearance of 30-50 mL per minute, the dose should be reduced to 50% or 0.75 mg/m² IV in the same schedule. The drug should not be used if clearance is less than 30 mL per minute.

Hepatic Insufficiency: Dose reduction is not required for liver dysfunction.

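### Four values in the 60 kg column of the creatinine clearance table contradict the formula printed beneath it, and the pentostatin section relies on that table

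*Combined protocol and SAP*

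**What the plan says.** Inclusion criterion 7 in Section 2.3.1 reads "Estimated creatinine clearance greater than 30 mL/minute (see Table 2.3.1"). The table has one row per serum creatinine value and weight columns 20 kg apart. Each cell gives male and female values, at ages 20/30/40 in the columns from 40 kg upward. The note below the table describes the formula as "Modified from Cockcroft Gault equation", prints it as (140 - age) x weight / (creatinine x 72), and adds "Females: 0.85 x the calculated result". A further note allows a calculated or measured clearance as an alternative.

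In the 60 kg column, the creatinine 1.2 row prints "Male 83/76/83 Female 59/65/71" and the creatinine 1.4 row prints "Male 71/66/60 Female 51/56/51".

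Section 2.4.5.6 states: "Pentostatin dose reductions for renal insufficiency are made based on estimated creatinine clearance (Table 2.3.1"). It ties a reduced dose to clearance of 30-50 mL/min and rules the drug out below 30.

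**The concern.** The creatinine 1.2 row looks wrong on its face. The formula falls with age, yet the female values at 60 kg rise from 59 to 71, and the male value at age 40 returns to the age-20 value of 83. Reading down the 60 kg column, a woman aged 20 has 51 at creatinine 1.4 but 53 at creatinine 1.6, so clearance improves as creatinine worsens.

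The table is more than illustrative. Section 2.4.5.6 names it for a dosing decision, and Section 2.4.5.1 says pentostatin leaves the body in urine mostly unchanged. If table and formula place the same patient in different renal bands, two sites could treat that patient differently while both follow the protocol.

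**Working it through.** **Inputs.** The formula and the 0.85 female factor come from the note under Table 2.3.1. The limits are 30 mL/min (Section 2.3.1) and 30-50 mL/min (Section 2.4.5.6).

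**Reproducing the table.** At 60 kg and creatinine 1.2 the divisor is 1.2 x 72 = 86.4.
- Male age 20: 120 x 60 / 86.4 = 83.3 (printed 83).
- Male age 30: 110 x 60 / 86.4 = 76.4 (printed 76).
- Female age 30: 76.4 x 0.85 = 64.9 (printed 65).

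Over the whole table, 186 of 190 printed values agree with the formula within rounding; the largest gap among them is 0.55 mL/min.

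**The four that do not reproduce** (all at 60 kg; the divisor at creatinine 1.4 is 1.4 x 72 = 100.8):

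| Creatinine, sex, age | Formula | Printed | Printed minus formula |
|---|---|---|---|
| 1.2, male, 40 | 100 x 60 / 86.4 = 69.4 | 83 | +13.6 |
| 1.2, female, 20 | 0.85 x 120 x 60 / 86.4 = 70.8 | 59 | -11.8 |
| 1.2, female, 40 | 0.85 x 100 x 60 / 86.4 = 59.0 | 71 | +12.0 |
| 1.4, female, 20 | 0.85 x 120 x 60 / 100.8 = 60.7 | 51 | -9.7 |

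The female line at creatinine 1.2 is the formula's series in reverse order.

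**At the tabulated weight, or by nearest column.** Printed against formula, the pairs are 83/69, 59/71, 71/59 and 51/61. All eight values exceed 50, so swapping one for the other changes no band.

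**By linear interpolation between 40 and 60 kg.** This is an assumption. The 40 kg cells are "Male 56/51/46 Female 47/43/39" at creatinine 1.2 and "Male 48/44/40 Female 41/37/34" at creatinine 1.4, and they agree with the formula within rounding. For weight w:

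| Creatinine, sex, age | Interpolated from printed cells | Reaches 50 at | Formula | Reaches 50 at | Table and formula disagree |
|---|---|---|---|---|---|
| 1.4, female, 20 | 41 + 0.50(w - 40) | 58.0 kg | 1.012w | 49.4 kg | 49.4-58 kg: table at or below 50, formula above |
| 1.2, female, 40 | 39 + 1.60(w - 40) | 46.9 kg | 0.984w | 50.8 kg | 46.9-50.8 kg: table above 50, formula below |
| 1.2, female, 20 | 47 + 0.60(w - 40) | 45.0 kg | 1.181w | 42.4 kg | 42.4-45 kg: table at or below 50, formula above |
| 1.2, male, 40 | 46 + 1.85(w - 40) | 42.2 kg | 1.157w | 43.2 kg | 42.2-43.2 kg: table above 50, formula below |

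For example, a woman aged 20 at 55 kg and creatinine 1.4 gets 41 + 0.5 x 15 = 48.5 from the table and 55.7 from the formula. A woman aged 40 at 50 kg and creatinine 1.2 gets 39 + 1.6 x 10 = 55 from the table and 49.2 from the formula.

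**Are the wrong cells the cause?** With the four cells set to 61, 59, 71 and 69, the interpolated lines reach 50 at 49.0, 51.0, 42.5 and 43.5 kg. Each is within about 0.4 kg of the formula, which is rounding. The wider ranges therefore come from the wrong cells, not from interpolation itself.

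**The 30 mL/min limit.** The lowest value on these four lines is 39, at 40 kg, so no reading between 40 and 60 kg approaches 30.

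**The case against.** The strongest reply is that nothing in the protocol sends a site through the steps needed for harm. No passage prescribes interpolation. The formula is printed directly under the table, a calculated or measured clearance is allowed, and applying the formula is no harder than interpolating by hand. The table stops at age 40, so older patients cannot be looked up in it at all. Three of the four ranges are only about 1 to 4 kg wide, and the 50 mL/min limit concerns one arm of four. All of this stands, and it limits the consequence. It does not remove the contradiction: the documents do not say which source governs when table and calculation disagree.

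A second reply is that a table taken from PDF text may be corrupted. That cannot be excluded from the text alone, although an exactly reversed series looks more like a typing error in the source. It is a reason to check the source table first.

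Two stronger readings are tempting. A reader might infer that the table as printed puts patients in the wrong pentostatin band. The documents do not support that without the interpolation assumption, because no wrong cell crosses 50 at its own weight or by nearest-column lookup. A reader might also infer, since the table sits under the inclusion criteria, that enrolment is affected. It is not, because the wrong values stay well clear of 30.

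**Conclusion.** Wrong as written, of minor severity. Four values in two serum creatinine rows (1.2 and 1.4) of the 60 kg column contradict the table's own formula by about 10 to 14 mL/min, and a dosing section cites the table. That part needs no assumption beyond the text matching the source table.

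A change of renal band is conditional. It requires a site to use the table rather than calculate, and to interpolate linearly in weight. It then runs in both directions over the ranges shown above, the widest about 8.6 kg (58 - 49.4). The sample size and operating characteristics are not affected.

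**What to change.** Check the four cells against the source table. If they stand there as printed here, correct them to agree with the formula: at 60 kg and creatinine 1.2, male age 40 to 69, female age 20 to 71 and female age 40 to 59; at 60 kg and creatinine 1.4, female age 20 to 61.

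Reconcile Sections 2.3.1 and 2.4.5.6 so that they state which clearance estimate (table, calculated or measured) applies to patients between or beyond the tabulated weights and ages. That choice, and the dose for each band, belong to the clinical team.

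The cost is four numbers and one agreed sentence.
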